### 13.3.3 Measurement at Follow-up Evaluation

The cytological confirmation of the neoplastic origin of any effusion that appears or worsens during treatment when the measurable tumor has met criteria for response or stable disease is mandatory to differentiate between response or stable disease (an effusion may be a side effect of the treatment) and progressive disease.

Cytologic and histologic techniques can be used to differentiate between PR and CR in rare cases (e.g., residual lesions in tumor types such as germ cell tumors, where known residual benign tumors can remain.)

## 13.4 Measurement of Effect

### 13.4.1 Target Lesions & Target Lymph Nodes

- Measurable lesions (as defined in [Section 13.2.1](#)) up to a maximum of 3 lesions, representative of all involved organs, should be identified as “Target Lesions” and recorded and measured at baseline. These lesions can be non-nodal or nodal (as defined in [Section 13.2.1](#)), where no more than 2 lesions are from the same organ and no more than 2 malignant nodal lesions are selected.

**Note:** If fewer than 3 target lesions and target lymph nodes are identified (as there often will be), there is no reason to perform additional studies beyond those specified in the protocol to discover new lesions.

- Target lesions and target lymph nodes should be selected on the basis of their size, be representative of all involved sites of disease, but in addition should be those that lend themselves to reproducible repeated measurements. It may be the case that, on occasion, the largest lesion (or malignant lymph node) does not lend itself to reproducible measurements in which circumstance the next largest lesion (or malignant lymph node) which can be measured reproducibly should be selected.
- Baseline Sum of Dimensions (BSD): A sum of the longest diameter for all target lesions plus the sum of the short axis of all the target lymph nodes will be calculated and reported as the baseline sum of dimensions (BSD). The BSD will be used as reference to further characterize any objective tumor response in the measurable dimension of the disease.

- Post-Baseline Sum of the Dimensions (PBSD): A sum of the longest diameter for all target lesions plus the sum of the short axis of all the target lymph nodes will be calculated and reported as the post-baseline sum of dimensions (PBSD). If the radiologist is able to provide an actual measure for the target lesion (or target lymph node), that should be recorded, even if it is below 0.5 cm. If the target lesion (or target lymph node) is believed to be present and is faintly seen but too small to measure, a default value of 0.5 cm should be assigned. If it is the opinion of the radiologist that the target lesion or target lymph node has likely disappeared, the measurement should be recorded as 0 cm.
- The minimum sum of the dimensions (MSD) is the minimum of the BSD and the PBSD.

### 13.4.2 Non-Target Lesions & Non-Target Lymph Nodes

Non-measurable sites of disease ([Section 13.2.2](#)) are classified as non-target lesions or non-target lymph nodes and should also be recorded at baseline. These lesions and lymph nodes should be followed in accord with [Section 13.4.3](#).

### 13.4.3 Response Criteria

All target lesions and target lymph nodes followed by CT/MRI/PET-CT/Chest X-ray/physical examination must be measured on re-evaluation at evaluation times specified in [Section 13.1](#). Specifically, a change in objective status to either a PR or CR cannot be done without re-measuring target lesions and target lymph nodes.

**NOTE:** Non-target lesions and non-target lymph nodes should be evaluated at each assessment, especially in the case of first response or confirmation of response. In selected circumstances, certain non-target organs may be evaluated less frequently. For example, bone scans may need to be repeated only when complete response is identified in target disease or when progression in bone is suspected.

#### Evaluation of Target Lesions

Complete Response (CR): All of the following must be true:

- Disappearance of all target lesions.
- Each target lymph node must have reduction in short axis to <1.0 cm.

Partial Response (PR): At least a 30% decrease in PBSD (sum of the longest diameter for all target lesions plus the sum of the short axis of all the target lymph nodes at current evaluation) taking as reference the BSD (*see* [Section 13.4.1](#)).

Progression (PD): At least one of the following must be true:

- At least one new malignant lesion, which also includes any lymph node that was normal at baseline (< 1.0 cm short axis) and increased to  $\geq 1.0$  cm short axis during follow-up.
- At least a 20% increase in PBSD (sum of the longest diameter for all target lesions plus the sum of the short axis of all the target lymph nodes at current evaluation) taking as reference the MSD ([Section 13.4.1](#)). In addition, the PBSD must also demonstrate an absolute increase of at least 0.5 cm from the MSD.
- See [Section 13.3.2](#) for details in regards to the requirements for PD via FDG-PET imaging.

Stable Disease (SD): Neither sufficient shrinkage to qualify for PR, nor sufficient increase to qualify for PD taking as reference the MSD.

**Evaluation of Non-Target Lesions & Non-target Lymph Nodes**

Complete Response (CR): All of the following must be true:

- a. Disappearance of all non-target lesions.
- b. Each non-target lymph node must have a reduction in short axis to <1.0 cm.

Non-CR/Non-PD: Persistence of one or more non-target lesions or non-target lymph nodes.

Progression (PD): At least one of the following must be true:

- a. At least one new malignant lesion, which also includes any lymph node that was normal at baseline (< 1.0 cm short axis) and increased to ≥ 1.0 cm short axis during follow-up.
- b. Unequivocal progression of existing non-target lesions and non-target lymph nodes. (**NOTE:** Unequivocal progression should not normally trump target lesion and target lymph node status. It must be representative of overall disease status change.)
- c. See [Section 13.3.2](#) for details in regards to the requirements for PD via FDG-PET imaging.

**13.4.4 Overall Objective Status**

The overall objective status for an evaluation is determined by combining the patient’s status on target lesions, target lymph nodes, non-target lesions, non-target lymph nodes, and new disease as defined in the following tables:

**For Patients with Measurable Disease**

| Target Lesions & Target Lymph Nodes | Non-Target Lesions & Non-Target Lymph Nodes | New Sites of Disease | Overall Objective Status |
|-------------------------------------|---------------------------------------------|----------------------|--------------------------|
| CR                                  | CR                                          | No                   | CR                       |
| CR                                  | Non-CR/Non-PD                               | No                   | PR                       |
| PR                                  | CR                                          | No                   | PR                       |
| PR                                  | Non-CR/Non-PD                               |                      |                          |
| CR/PR                               | Not All Evaluated*                          | No                   | PR                       |
| SD                                  | CR                                          | No                   | SD                       |
| SD                                  | Non-CR/Non-PD                               |                      |                          |
| SD                                  | Not All Evaluated*                          |                      |                          |
| Not all Evaluated                   | CR                                          | No                   | Not Evaluated (NE)       |
| Not all Evaluated                   | Non-CR/Non-PD                               |                      |                          |
| Not all Evaluated                   | Not All Evaluated*                          |                      |                          |
| PD                                  | Unequivocal PD                              | Yes or No            | PD                       |
| PD                                  | CR                                          |                      |                          |
| PD                                  | Non-CR/Non-PD                               |                      |                          |
| PD                                  | Not All Evaluated*                          |                      |                          |
| CR/PR/SD/PD/Not all Evaluated       | Unequivocal PD                              | Yes or No            | PD                       |
| CR/PR/SD/PD/Not all Evaluated       | CR                                          | Yes                  | PD                       |
| CR/PR/SD/PD/Not all Evaluated       | Non-CR/Non-PD                               |                      |                          |
| CR/PR/SD/PD/Not all Evaluated       | Not All Evaluated*                          |                      |                          |

\* See [Section 13.4.3](#)

### 13.4.5 Symptomatic Deterioration

Patients with global deterioration of health status requiring discontinuation of treatment without objective evidence of disease progression at that time, and not either related to study treatment or other medical conditions, should be reported as PD due to “symptomatic deterioration.” Every effort should be made to document the objective progression even after discontinuation of treatment due to symptomatic deterioration. A patient is classified as having PD due to “symptomatic deterioration” if any of the following occur that are not either related to study treatment or other medical conditions:

- Weight loss >10% of body weight.
- Worsening of tumor-related symptoms in the opinion of the treating physician.
- Decline in performance status of >1 level on ECOG scale.

## 14.0 REMOVAL OF PATIENTS FROM PROTOCOL THERAPY

### 14.1 Clinical Follow-Up Phase

- Patients who are in complete response (CR), partial response (PR), or stable disease (SD) will receive treatment indefinitely and until progression (PD) or unacceptable adverse events. Subsequent off-study treatment is at the discretion of their attending physician. See [Section 13.4](#) for the criteria for assessing response.
- Patients who discontinue for non-PD reasons and prior to 1 year post-randomization will remain in Clinical Follow-Up until they have reached 1 year post-randomization. Thereafter, they will begin the Survival and Disease Status Follow-Up Phase.
- Patients on the placebo arm may cross over to the sorafenib arm, upon PD, and continue in Clinical Follow-Up. Patients who undergo surgical excision of their tumors must start sorafenib within 28 days of surgery. After excision, the patient must have measureable disease (per RECIST v1.1). Patients will begin Survival and Disease Status Follow-Up upon subsequent PD.
- Patients on the sorafenib arm will begin Survival and Disease Status Follow-Up upon PD.
- As of Update #06: Patients unblinded following the Alliance Data Safety Monitoring Board release of study data (November 17, 2017) while receiving placebo and prior to PD, may cross over to the sorafenib arm and continue in Clinical Follow-Up. Patients who undergo surgical excision of their tumors must start sorafenib within 28 days of surgery. After excision, the patient must have measurable disease (per RECIST v1.1). Patients will begin Survival and Disease Status Follow-Up upon subsequent PD.

### 14.2 Survival and Disease Follow-Up Phase

During the Survival and Disease Follow-Up Phase, patients are monitored for off-treatment PD, long-term adverse events, new primaries, and survival. Here, patients should be followed per standard of care. Submit the appropriate form(s), every 6 months until PD. Thereafter, annually until a maximum of 3 years following randomization.

### 14.3 Managing ineligible and canceled patients and major protocol violations

Data must be submitted per [Section 6.0](#) for patients deemed ineligible or canceled. See also the Forms Packet for full details of data submission requirements.

#### 14.4 Extraordinary Medical Circumstances

If, at any time the constraints of this protocol are detrimental to the patient's health and/or the patient no longer wishes to continue protocol therapy, protocol therapy shall be discontinued. In this event:

- Notify the Study Chair.
- Document the reason(s) for discontinuation of therapy on study forms
- Follow the patient for survival or secondary malignancy for a minimum of 3 years following randomization.

### 15.0 STATISTICAL CONSIDERATIONS

#### 15.1 Primary Endpoint

We are comparing the progression-free survival (PFS) rate of patients will receive either sorafenib or placebo in and using randomized double-blinded placebo controlled phase 3 study design. PFS is defined as the time from randomization to the first occurrence of progression or death due to any cause. If no event exists, the PFS will be censored at the last scheduled disease assessment on study. Patients who have reached their maximum follow-up and have remained progression-free will be censored for progression at the date of their last disease assessment. Data following cross over will be analyzed and summarized separately from the data from the main course of treatment for these patients. Intention to treat principles will be used for analyzing the primary endpoint, excluding patients deemed ineligible due to improper histology having been determined on the basis of information available prior to randomization.

Update #06: Patients enrolled onto this trial were unblinded (November 17, 2017) and those receiving placebo were allowed to crossover to sorafenib, if PD had not yet occurred. This section has been updated to address this for the analysis.

##### 15.1.1 Sample Size & Statistical Power

The placebo (control) arm is expected to have a median PFS of 6 months. We consider improving PFS to a median of 15 months (HR of 0.40, control versus experimental arm) after treatment with sorafenib (experimental arm) to be a significant clinical improvement of PFS in this patient population. We will be using a 1-sided Log-Rank test to determine the whether sorafenib significantly improves the PFS rate. We have designed this study with one planned interim analysis which is designed to stop the trial for “futility” and there is no interim analysis for efficacy. We are also using a 2:1 randomization scheme to increase accrual for the as well as to reduce the number of patients having biopsies while receiving treatment on a placebo arm. There are two stratification factors for randomization and in addition to randomizing membership, namely, Intra- versus Extra-abdominal disease, and Baseline Level of Pain (BPI Item #3: 0 to <3, 3 to <7, versus 7 to 10).

Using 75 patients, we have 90% power at a 1-sided significance level of 0.025 to detect a median PFS 15 months (Ho: median PFS of 15 months for sorafenib) improvement over the placebo arm (Ho: median PFS of 6 months, resulting in a HR=0.40), using a 2:1 randomization favoring the sorafenib arm, assuming we will enroll 4 patients per month, and requiring 12 months of follow-up for all patients. There is 50% chance of terminating the study for futility at the time of the interim analysis if the true median PFS in the sorafenib arm is 6 months. The other type of decision error we could make based on our sample is if we were declare sorafenib as ineffective (ie, “accept” Ho), when in fact the truth is that is effective in our sampling population. In this situation, we have a 1.39% chance of stopping for futility (ie, declaring sorafenib ineffective) at the interim analysis if the median PFS for the sampling population is 15 months.

**Decision Rule:** We will randomize a total of 75 patients (25-placebo, 50-sorafenib) and observe patients until we have reached 52 PFS events for the efficacy analysis. In the event the median PFS in the control group is larger than expected and long-term follow-up becomes a concern, we will perform the final efficacy analysis after 52 events are observed or after all evaluable patients have been followed for at least 3 years, whichever occurs earlier. If the 1-sided p-value associated with the Log-Rank test is  $< 0.0255$  (corresponding to an observed HR of 0.5776), we will consider sorafenib as having shown promising activity in this population and may recommend it for further testing.

**Inefficacy/Futility Analysis:** We will evaluate the observed PFS of the arms when 45% of the PFS events required for the final efficacy analysis (i.e., 24) have been observed.

We will terminate the study for futility if the p-value associated with the test statistic from a Log-Rank is at least 0.5025 (corresponding to an observed HR of 1.0027). Otherwise, we will continue to complete full enrollment.

Although the primary endpoint will be evaluated using the first 75 evaluable patients, final efficacy results will further report results (e.g., publication, presentation) using all patients evaluable for determining PFS and so that patient enrolled beyond these 75 may contribute to these estimates.

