## 5.6 Stratification

Patients will be stratified at randomization by:

- 1) intra-abdominal disease: yes vs no

2) baseline level of pain (BPI “Worst Pain” Item: 0-<3; 3 – <7 vs 7 – 10). See [Appendix V](#).

We will be using a 2:1 randomization scheme to improve accrual to the study given that it has an observation arm and to also reduce biopsies performed for patients who have been enrolled to the placebo group. The randomization algorithm used by the Alliance Statistics & Data Center uses dynamic allocation procedure which balances the marginal distributions of the stratification factors between treatment regimens.

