#### **15.2.2 Surgical Intervention**

Surgical excision/amputation is a therapeutic and palliative options for managing this disease. Time to surgical intervention during treatment is defined as time between randomization to the patient undergoing therapeutic surgical resection for this disease. If no event exists, patients will be censored at their date of last treatment for this event. A log rank test will be used to compare the distributions of time to surgical intervention between the two arms using a 2-sided test and  $\alpha=0.05$  level of significance. Kaplan-Meier (1958) methodology will be used to estimate various time points (e.g. 1 year rate, 2 year rate, etc.) and 95% Confidence Intervals will be calculated for these estimates. Surgery will be classified by outcome (e.g. complete-macroscopic, complete-microscopic, or partial), type, location (e.g. limb), thereafter analyzed by categorical analysis and descriptive statistics. Non-parametric methods will be used, as appropriate. See the note at the beginning of [Section 15.2](#).

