#### **15.2.4 Tumor Response**

Patients will be classified for disease status according to RECIST v1.1 (see [Section 13.0](#)). We will compare best objective status for the two treatment arms and using the Cochran-Mantel-Haenszel test. Duration of response will be calculated as the time between first tumor response and progression. Patients will be censored for duration of response at the date of last assessment if they have reached maximum follow-up without PD (or are lost to follow-up without PD). Kaplan Meier methodology will be used to estimate the distribution of duration of response and the Log-Rank test will be used to test for a difference in duration of response between the two arms. See the note at the beginning of [Section 15.2](#).

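### For PFS and the section 15.2 efficacy endpoints, no analysis is stated to use the factors balanced at randomisation: say how the tests are stratified and add labelled supportive analyses

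*Combined protocol and SAP*

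**What the plan says.** Section 5.6 stratifies randomisation by two factors, "intra-abdominal disease: yes vs no" and baseline worst pain in three levels, with a 2:1 dynamic allocation that balances their margins. Section 15.1.1 repeats the two factors with this wording: "There are two stratification factors for randomization and in addition to randomizing membership". It identifies the pain factor as "BPI Item #3: 0 to <3, 3 to <7, versus 7 to 10". Section 5.6 lists no membership factor, and Appendix V calls the pain item question #1.

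The primary test is described only as follows: "We will be using a 1-sided Log-Rank test to determine the whether sorafenib significantly improves the PFS rate". The final boundary is a one-sided p below 0.0255, "corresponding to an observed HR of 0.5776". For the interim look: "We will terminate the study for futility if the p-value associated with the test statistic from a Log-Rank is at least 0.5025". Neither passage names a stratum.

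Section 15.2 is equally silent. For surgery (15.2.2): "A log rank test will be used to compare the distributions of time to surgical intervention between the two arms". For response (15.2.4): "We will compare best objective status for the two treatment arms and using the Cochran-Mantel-Haenszel test". The overall survival log-rank (15.2.3) and the duration-of-response log-rank (15.2.4) name no stratum either. No Cox or other adjusted model is planned for any of these endpoints. Section 15.1.6 considers only an analysis without cases found discordant on central review, and censoring at surgery or radiotherapy.

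The patient-reported outcomes differ. Section 15.3.2 compares each between arms by analysis of covariance and by a mixed model, both adjusted for the baseline score.

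**The concern.** The trial balances two factors by design and then states no use for them in the analysis of PFS, time to surgery, survival or response. Two things follow.

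First, a reader cannot tell whether the log-rank test is stratified, and the two versions can fall on different sides of 0.0255. Second, if either factor is prognostic, an unstratified log-rank loses power and estimates an HR closer to 1, and the plan has no adjusted estimate to set beside it.

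For response, a CMH test is normally defined by its strata. With none, its general-association statistic is the Pearson chi-square times (N−1)/N, which is 74/75 = 0.987 here. Section 1.10 reports, from a retrospective series, that partial response and stable disease were mostly seen in extra-abdominal tumours (p=0.03). Intra-abdominal disease is therefore the natural stratum to name.

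**Working it through.** **Inputs from the plan (15.1.1).** 75 patients (50 sorafenib, 25 placebo), 52 events, medians 6 and 15 months (HR 0.40), 4 patients per month, one-sided alpha 0.025, final boundary 0.0255, futility look at 24 events.

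**The plan's own figures.**
- *Power, stated as 90%.* The Schoenfeld formula with the 2:1 allocation gives Φ(|ln 0.40| × √(52 × 2/9) − 1.960) = Φ(3.115 − 1.960) = 87.6%. Simulating an unstratified log-rank at the 52nd event gives 89.8% at 0.025 and 90.2% at 0.0255, so the 90% reproduces.
- *Futility HR.* exp(0.00627/√(24 × 2/9)) = 1.0027, as printed.
- *Final HR.* (1.9515/|ln 0.5776|)² = 12.64, and 12.64/52 = 0.243 per event. That matches 52 events split about 21.7/30.3.

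**Simulation.** 20,000 trials per scenario: 2:1 minimisation on both margins, exponential PFS, analysis at 52 events, one-sided p<0.0255, no futility stop. Monte Carlo SE is about 0.2 to 0.3 point. Intra-abdominal disease is 50%, following 15.3.1. Pain is 30/35/35%. Section 15.3.2 expects about 70% evaluable for an analysis that needs pain of at least 3, so at most about 30% fall below 3; the remaining split is assumed. All prognostic HRs are assumptions, because the documents give none for PFS.

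Power (%) at treatment HR 0.40:

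| Disease HR, HR per pain level | Unstratified | By disease | Six cells | Cox by disease, adjusted for pain |
|---|---|---|---|---|
| 1, 1 | 90.2 | 89.6 | 85.8 | 89.4 |
| 1, 1.5 | 87.2 | 86.7 | 85.7 | 88.9 |
| 1, 2 | 81.9 | 81.1 | 85.1 | 88.5 |
| 1.5, 1.25 | 88.2 | 88.8 | 85.7 | 89.4 |
| 2, 1 | 87.3 | 89.6 | 86.0 | 89.3 |
| 2, 1.3 | 86.6 | 88.7 | 86.3 | 89.3 |
| 2, 2 | 78.9 | 81.0 | 85.2 | 88.4 |
| 2.5, 1.5 | 81.8 | 86.4 | 85.5 | 88.6 |

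- Stratifying by disease gains 2.1 to 4.6 points at disease HR 2 to 2.5 and loses 0.5 to 0.8 point at disease HR 1.
- Six cells cost 90.2 − 85.8 = 4.4 points when neither factor matters. They average 75/6 = 12.5 patients and 25/6 = 4.2 placebo patients each.
- The median estimated HR is 0.40 to 0.47 unstratified and 0.39 adjusted.
- The unstratified and disease-stratified tests disagree at 0.0255 in 2.1% of trials at (1, 1), 4.4% at (2, 1) and 6.9% at (2.5, 1.5).
- Type I error against nominal 2.55% is 1.9 to 3.2% unstratified, 2.0 to 3.2% by disease and 3.0 to 3.4% for the Cox Wald test.

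**Robustness.** A separate simulation gave, unstratified against disease-stratified, 89.0/88.1% at (1, 1), 85.6/88.4% at disease HR 2 and 81.1/85.6% at (2.5, 1.5). Recording progression at 8-weekly scans gave 89.6/89.1% at (1, 1) and 87.0/89.2% at (2, 1). If crossover censoring left only 40 events (an assumption), the figures were 81.2/80.6% and 78.9/81.2%.

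**CMH.** Binary response, two-sided 0.05, 37 intra- and 38 extra-abdominal patients, single table against stratified by disease:
- 25% vs 5% (sorafenib vs placebo) in both groups: 62.6 vs 62.8%.
- Extra/intra-abdominal 40/10% on sorafenib and 10/2% on placebo: 55.5 vs 59.4%.
- Extra/intra-abdominal 60/20% on sorafenib and 25/5% on placebo: 59.9 vs 68.5%.

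The 25% is 6/24 from section 1.10. The other rates are assumed.

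**The case against.** A reader might infer that no efficacy analysis anywhere uses the balanced factors. Section 15.3.2 does not support that. Its covariance and mixed models adjust worst pain for its baseline score, which is one of the two factors, and section 10.2 calls patient-reported outcomes a key secondary endpoint. The gap is confined to PFS and section 15.2.

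A reader might also infer from the reproduced power and HRs that the planned log-rank is unstratified. The figures cannot show this. With no prognostic effect, 90.2% and 89.6% both round to 90%. The printed HRs come from planning formulas with no stratum term, and they imply different variance factors (0.243 at the final analysis, 2/9 = 0.222 at futility). Simulated variance per event at HR 0.40 was 0.174 unstratified and 0.173 by disease with no prognostic effect, and 0.177 and 0.170 at disease HR 2. Only the six-cell version is disfavoured. The unnamed CMH stratum could likewise already be a randomisation factor.

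Other objections also stand in part:
- The disease-stratified test is slightly weaker when only pain is prognostic.
- Tests disagree in 2.1% of trials even when neither factor matters, so not all of the 2 to 7% reflects prognosis.
- The link in section 1.10 is thin. Partial response plus stable disease is 6 + 17 = 23 of 24 patients, and it says nothing about PFS.
- Best objective status has several levels, so a binary simulation only indicates the gain.
- The pain label is a numbering matter, since the cut-points agree.

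None of this supplies the missing adjusted estimate or names the strata.

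**Conclusion.** The point holds as a minor, low-cost improvement. For PFS and the section 15.2 efficacy endpoints, no analysis is stated to use the factors balanced at randomisation. The planned log-rank remains valid. A reader might suspect that omitting the factors inflates the false-positive rate, but the simulations do not show it: the unstratified rate was highest with non-prognostic factors, where stratified tests were similar, and it fell as the factors became more prognostic.

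The cost is a power loss of about 2 to 5 points against disease stratification at an assumed disease HR of 2 to 2.5, with the HR drawn toward 1. The difference is under 1 point the other way if disease is not prognostic. For response, the gain from naming the stratum is 0 to about 9 points, for a binary outcome under assumed rates. These sizes rest on assumed prognostic effects, exponential PFS and an assumed pain distribution. Equal thirds for pain moved power by at most about 1.2 points and did not change the ordering.

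**What to change.** 1. **Section 15.1.1.** Keep the primary and futility log-rank tests and their boundaries. State whether each was intended as stratified or unstratified. Sections 14.1 and 15.1 record the release of study data and the unblinding on November 17, 2017, so the test should not be re-chosen now.
2. **Supportive PFS analyses.** Fix these in writing before they are run and label them as added after that release: (a) a log-rank stratified by intra-abdominal disease; (b) an HR with 95% CI from a Cox model stratified by intra-abdominal disease and adjusted for the pain category used at randomisation. Do not cross all six cells. Present the Cox result as an estimate, not a decision test, because its Wald test is slightly liberal at this size.
3. **Section 15.2.4.** Run the CMH test of best objective status stratified by intra-abdominal disease, with the same post-release label unless that stratum was already intended.
4. **Sections 15.2.2 to 15.2.4.** State the strata, or that there are none, for the time-to-surgery, survival and duration-of-response log-rank tests.
5. **Clarifications.** Reconcile the pain item's label across 5.6, 15.1.1 and Appendix V, and say whether the membership phrase in 15.1.1 denotes a further balancing factor.

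The cost is a few sentences, two extra PFS outputs and a named CMH stratum, using factors already recorded at registration. Sample size, event count and decision rule do not change.
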